10.2 Labeling

Investigational agents will be packaged by a central pharmacy and distributed to investigational sites in individual patient cartons. BUP/NX will be packaged in childproof blister packs. This is an open-label study and blinding of investigational agents is not necessary.

10.3 Record of Administration

Accurate recording of all investigational agents dispensed, prescribed or administered will be made.

11.0 STUDY PROCEDURES

Table 1 summarizes the timing of study procedures and clinical assessments.

11.1 Initial Patient Screening

Program staff at each CTP will be thoroughly trained in the protocols in operation at their site, and specifically regarding the inclusion and exclusion criteria detailed in section 9.0. Patients will be recruited through IRB-approved newspaper and poster advertisements, and/or by word-of-mouth. Additionally, any patients calling or walking into the clinic will be advised of the availability to participate in the research protocol. Potential patients contacting the CTP will respond to the CTP's standard screening/intake questionnaire. This screening questionnaire will permit evaluation of the study's inclusion criteria. Potential patients that are identified as meeting the inclusion criteria will be provided basic information about the research protocol and, if interested, provided with an appointment for the purposes of obtaining informed consent and baseline assessments. Any patients deemed ineligible for the research study during the initial patient screening or following baseline assessment will be referred to standard treatment services within the CTP or at another local treatment facility.

11.2 Informed Consent

Prior to the collection of any baseline assessments or initiation of any research procedures, the Study Coordinator (or person assuming this role) at each CTP will obtain informed consent for study participation (see Appendix II for an example Informed Consent Form). Adults, or legally emancipated minors will be provided with a consent form describing the study's purpose, general procedures, risks and benefits along with the patient's role in the study. Additionally, the consent procedure informs patients that descriptive information about them obtained during the baseline assessment on the Basic Data and Locator Questionnaires may be shared with outreach workers at the CTP to facilitate finding patients for follow-up evaluations. The consent form will also specify that neither buprenorphine-naloxone or clonidine has been approved by the FDA for opiate detoxification. The consent form is valid for 14 days in the event the participant requires re-assessment during baseline. (See section 11.3)

*Special Consideration for NW node: For CTPs requiring a 24-hour period between the receipt of informed consent and signing, baseline assessments or initiation of research procedures should occur following the signing of the informed consent.

Informed consent procedure for minors (15 - 17 years-of-age): All minors (except for those legally "emancipated") will be required to (a) have parental/guardian consent and (b) provide their assent to participate in the studies.

TABLE 1. TIME AND EVENTS SCHEDULE-CORRECTED COPY

| Activity | Screening/ | Study Interventions | | | | | | | | | | Follow-up | | | | | | |
|------------------------------|------------|--|----|----|----|----|----|----------------------------|----|----|----|-----------|----|----|----|---|---|----------|
| | Baseline | (study days) *** 1 2 3 4 5 6 7 8 9 10 11 12 13 14 | | | | | | (months since study start) | | | | | | | | | | |
| Time | | | | | | _ | | | | | | | | | 14 | 1 | 3 | 6 |
| Detoxification | | X | X | X | X | X | X | X | X | X | X | X | X | X | | | |   |
| Screening Assessments | | | | | | | | | | | | | | | | | | |
| Informed Consent | X | | | | | | | | | | | | | | | | | |
| Demographics | X | | | | | | | | | | | | | | | | | |
| DSM-IV Checklist | X | | | | | | | | | | | | | | | | | |
| Psychiatric eval. (ASI Lite) | X | | | | | | | | | | | | | | | | | |
| Medical History | X | | | | | | | | | | | | | | | | | |

11.3 Baseline Assessments

Baseline assessments will consist of a comprehensive assessment of addiction severity and withdrawal status, medical and psychiatric status and assessment of HIV risk. The interview will consist of the psychoactive substance abuse disorder sections of the DSM-IV Criteria Checklist (modified from Hudziak et al., 1993) and an abbreviated version of the fifth edition of the ASI known as the ASI Lite (McLellan et al., 1985). Additional questionnaires will also be completed to provide information about demographics and drug history including any concomitant medications received either over the counter or by prescription as well as level of opioid withdrawal being experienced by the patient. Medical status will be determined by medical history, physical exam and laboratory evaluation (including complete blood count, clinical chemistry profiles, serology for Hepatitis B and C, urinalysis, and urine screen for drugs of abuse). The physical examination will include vital signs and ECG for all patients. On or off-site HIV testing and HIV counseling will be encouraged.

Female patients will be required to have a pregnancy test prior to receiving their first dose of investigational agents. Female patients of childbearing potential (including gay women patients who have sex with men) will also be required to practice acceptable birth control (e.g., oral or depo contraceptives, foam, sponges, and condoms). The birth control method will be documented on a CRF. Women who become pregnant will be withdrawn from the study and given immediate access to methadone maintenance services at the CTP or another local treatment provider. Patients refusing methadone maintenance will be referred to another local provider, preferably one providing specialized services for pregnant or post-partum women.

Before entering the in-patient facility, patients will be instructed not to use any heroin or other opiate drugs for at least 6 hours prior to the time scheduled to receive their first dose of study agent and to be in mild withdrawal before taking their first dose. Study coordinators at each study site will take a history from the patient prior to administration of the first dose of study agent to document the time and data of last drug use and verify patient withdrawal status.

Generally patients should only be assessed once to determine if they meet all of the inclusion and none of the exclusion criteria for study participation. However, there may be extenuating circumstances when a patient would become eligible if they could be partially reevaluated on another day. For example, if the only item precluding randomizing the patient was a methadone positive urine test result, the patient could be brought back on the next or subsequent day(s), and another Accutest Screen for opiates, methadone and COWS assessment could be conducted to determine whether they could now be a participant. Another example would be if the patient were eligible except for their reporting having been in methadone/LAAM treatment within the last 30 days. The patient could be brought back at another time when 30 days would have elapsed and another quick test and COWS assessment could be performed provided this was done within 14 days of originally consenting the participant to the study.

In any case, patients should only be reassessed under extraordinary circumstances in which it is obvious that with an additional Accutest Screen for methadone and opiates and a COWS assessment, the individual would likely be eligible to participate and this can be accomplished within 14 days or less from the time of the original consent.

11.4 Randomization And Enrollment

To qualify for the study, patients are required to meet all inclusion/exclusion criteria. A patient will be included in the study after having been examined by the investigator or study physician who verifies that the inclusion criteria are met and no exclusion criteria are present.

Patients will be assigned randomly once it is determined that eligibility criteria have been met. Randomization to groups will be performed within each site (CTP). Data management for the Pacific Region Node will create randomization envelopes for each site that will be distributed prior to study initiation.

Approximately 60 patients will be enrolled at each of the participating CTP sites for a total of 360 patients. Patients will be assigned to the BUP/NX and clonidine groups using a 2:1 ratio of random assignment. That is, for every patient assigned to receive clonidine, two patients will be assigned to receive BUP/NX. This 2:1 ratio of assignment should facilitate recruitment into the protocols given that patients will have a 66% chance of being assigned to receive BUP/NX. Moreover, the 2:1 assignment will facilitate acquisition of data in a larger cohort of patients on the use of BUP/NX for short-term opiate detoxification.

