8.0 STUDY DESIGN

A randomized, open-label, parallel groups study design will be used. After screening and baseline assessments, patients will be stratified for gender and randomly assigned in a 2:1 ratio to either a BUP/NX or clonidine 13-day detoxification. Patients will initiate detoxification in the inpatient setting and, as necessary, will continue detoxification as outpatients for the full 13 days. This typically ranges from 5 to 13 days of inpatient detoxification. After the 13 day detoxification, patients will be assessed for outcome measures including relapse and withdrawal symptoms at follow-up visits occurring 1, 3, and 6 months after starting detoxification. Counseling procedures in existence at each CTP will be used throughout the study. Self-help detoxification handbooks will be distributed to all study participants.

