14.0 ANALYTICAL PLAN

14.1 Statistical Hypotheses

Primary Efficacy Endpoint: It is hypothesized that BUP/NX detoxification, compared to clonidine, will be associated with a better treatment response. A treatment responder is defined as anyone who completes the 13-day detoxification and whose last urine specimen is negative for opiates. By combining treatment retention with opiate abstinence, a composite number is derived that is indicative of both the patients' tolerance to the treatment and the desired outcome of abstinence at the completion of a short-term detoxification procedure. Note that there is no issue concerning the handling of missing data when utilizing this definition of "responder." Patients who fail to either come in or provide a urine sample are, by definition, non-responders.

Other Primary Efficacy Endpoint: Other primary efficacy endpoints were selected to examine the effect of treatment on 1) opiate and other drugs of abuse abstinence throughout the detoxification period and during longer term follow-up, 2) withdrawal symptoms, 3) treatment retention, 4) safety, 5) patient satisfaction with the treatment and 6) extent of ancillary medications dispensed to provide a comprehensive overview of the clinical efficacy and safety of the two treatment regimens.

Hypotheses for the other primary outcome measures include that BUP/NX detoxification, compared to clonidine, will:

- 1. Increase the number and consecutive duration of opiate and all drug-free urine specimens during detoxification and follow-up.
- 2. Increase the number of days retained in treatment.
- 3. Decrease the amount of ancillary medications needed to treat withdrawal symptoms.
- 4. Lessen the severity of withdrawal symptoms as assessed by COWS, ARSW, and VAS.
- 5. Lessen the severity of dependence or abuse as assessed by ASI Lite.

6. Improve the quality of life as assessed by the SF-36 questionnaire and satisfaction with treatment (CSQ).

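### Section 11.4 lets open-label assignment happen as soon as eligibility is confirmed, so nothing requires the envelope to stay closed until the patient is admitted and ready for the first dose

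*Protocol*

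**What the plan says.** Section 8.0 sets the design: "A randomized, open-label, parallel groups study design will be used". Section 11.4 sets the moment of assignment: "Patients will be assigned randomly once it is determined that eligibility criteria have been met". It uses envelopes distributed to each site before the study starts, and it names no later step that must be complete before an envelope is opened.

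Other sections describe what surrounds that moment:

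- **11.1:** a potential patient who seems to qualify and is interested is "provided with an appointment for the purposes of obtaining informed consent and baseline assessments".
- **11.3:** "Before entering the in-patient facility, patients will be instructed not to use any heroin or other opiate drugs" for at least 6 hours before the scheduled first dose, and "to be in mild withdrawal before taking their first dose". Site staff verify withdrawal status before that dose. Section 11.5.1 repeats this for BUP/NX, with the COWS and ARSW as the check.
- **14.2.1 and 14.3:** the primary outcome counts responders out of all patients randomised to the arm, dosed or not.
- **14.1:** "Patients who fail to either come in or provide a urine sample are, by definition, non-responders".
- **14.4:** the primary outcome is not analysed in the evaluable population. That population (14.3) requires completion of the 13 days in any case.

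**The concern.** As 11.4 is worded, a site may open the envelope once eligibility is settled, while admission, the opiate-free hours and the withdrawal check are still to come. Another site may open it minutes before dosing. Both comply.

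The assignment is not masked, so any interval gives a patient time to act on it before taking any drug. A patient who leaves then is a non-responder under 14.1. If leaving is equally common in the two arms, the rates are diluted slightly and no false difference arises. If it is more common in the clonidine arm, the primary comparison contains a reaction to the assignment as well as the effect of the regimen, and the bias favours BUP/NX. Section 14.1 presents the endpoint as reflecting tolerance of treatment together with abstinence. Refusal before any dose is neither.

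**Working it through.** The protocol gives no figure for departures between assignment and first dose, so there is no stated value to reproduce. The check asks how large the distortion would be over a range of assumed departures.

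**Inputs from the protocol:** 240 BUP/NX and 120 clonidine patients, and a planned difference of 10 points, 30% against 20% (14.6); chi-square test, two-sided alpha 0.05 (14.4). The power stated in 14.6 is not used.

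**Assumed inputs:** true response r = 25% among starters in both arms (no drug difference; midway between the two planning rates); share leaving before the first dose d_B = 2% on BUP/NX; d_C = 5%, 10% or 20% on clonidine, which is 6, 12 or 24 of 120 patients.

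**Observed rate in an arm** = r × (1 − d), because those who leave are counted as non-responders:

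- BUP/NX: 0.25 × 0.98 = 24.5%
- Clonidine: 0.25 × 0.95 = 23.75%; 0.25 × 0.90 = 22.5%; 0.25 × 0.80 = 20.0%

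**Chance of a significant result:** add the binomial probabilities of every pair of responder counts (x_B of 240, x_C of 120) for which |z| > 1.96, where z = (x_B/240 − x_C/120) / √[p(1 − p)(1/240 + 1/120)] and p = (x_B + x_C)/360.

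| Leaving, BUP/NX vs clonidine | Observed rates | False difference (share of the planned 10 points) | Wrongly favours BUP/NX | Wrongly favours clonidine | Total two-sided error |
|---|---|---|---|---|---|
| 0% vs 0% | 25% vs 25% | 0 | 2.4% | 2.6% | 5.0% |
| 2% vs 5% | 24.5% vs 23.75% | 0.75 points (7.5%) | 3.4% | 1.8% | 5.2% |
| 2% vs 10% | 24.5% vs 22.5% | 2.0 points (20%) | 5.8% | 0.9% | 6.7% |
| 2% vs 20% | 24.5% vs 20.0% | 4.5 points (45%) | 15.1% | 0.2% | 15.3% |

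**Sensitivity to the common response rate** (normal approximation, no leaving on BUP/NX): the chance of wrongly favouring BUP/NX with 5%, 10% or 20% clonidine leaving is 4.0%, 6.3% or 14.1% at a common response of 20%, and 4.7%, 8.3% or 21.6% at 30%.

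The distortion is small when the arms differ by a few points in leaving. It becomes material from about 10% clonidine leaving.

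**The case against.** A reader might infer that the protocol schedules assignment ahead of admission. It does not say so, and several places fit same-day sequencing. Inclusion criterion 1 already requires reported withdrawal symptoms. Section 11.3 makes a repeat COWS part of any re-evaluation of eligibility. ECG reports return within two hours to speed inclusion decisions (12.8). Follow-up is counted from enrolment in 11.9 and from the start of detoxification in 8.0, as though the two coincide. This objection stands: the fault is that nothing requires the close sequence, not that a gap is planned.

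A reader might also take the sentence that the 2:1 ratio "should facilitate recruitment into the protocols given that patients will have a 66% chance of being assigned to receive BUP/NX" as evidence that patients who draw clonidine will leave. It concerns willingness to enrol. It makes a preference for BUP/NX plausible, but it says nothing about conduct after assignment, and these patients have consented to either treatment.

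Nor is it right that the effect could never be separated afterwards. Daily amounts administered are logged (12.19), reasons for withdrawal go on a CRF (13.3), and retention over time is summarised by arm (14.5). Never-dosed patients can therefore be identified. An analysis restricted to dosed patients no longer compares the groups as randomised, though, so it can support the primary result but not replace it.

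Finally, counting every randomised patient is a legitimate choice in an open-label comparison of clinical utility, and acceptability is arguably part of utility. That also stands, and the intent-to-treat analysis should not change. But time spent waiting between envelope and first dose is a product of trial procedure, and acceptability can be judged without it.

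**Conclusion.** The point holds as a cheap improvement to the wording of 11.4. It does not show that the trial is biased. The documents support three statements: assignment may occur at confirmed eligibility, later pre-dose steps are not made a condition of it, and everyone assigned counts in the denominator. The direction of the bias depends on clonidine patients leaving more often, which is plausible but not documented.

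The size rests wholly on assumed leaving rates. With 25% response among starters in both arms and 2% leaving on BUP/NX, the chance of wrongly favouring BUP/NX is 3.4%, 5.8% or 15.1% for 5%, 10% or 20% leaving on clonidine, against 2.4% with none. Total two-sided error barely moves in the mildest case. If every site already opens the envelope immediately before dosing, the change costs nothing and alters nothing.

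**What to change.** In 11.4, state that the envelope is opened only as the last step before the already scheduled first dose, after the patient has been admitted, withdrawal status has been verified and the pre-dose COWS, ARSW and VAS have been recorded. Record the time of opening and the time of first dose. Report patients randomised but never dosed by arm, and add a supportive analysis of the primary outcome in dosed patients. Keep the intent-to-treat analysis primary.

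The cost is a sentence in the protocol, two recorded times and one supportive table. The steps already exist and only their order is fixed. A few eligible patients who never arrive will not be randomised. Departures after the envelope is opened remain possible and still count as non-response, so the change reduces the problem without removing it. It sets no dosing or treatment-timing rule.

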11.5 Study Interventions

11.5.1 BUP/NX

To facilitate a comfortable transition onto the BUP/NX combination tablet, patients will be instructed not to use any heroin or other opiate drugs for at least 6 hours prior to receiving their first dose of BUP/NX and to be in mild withdrawal before taking their first dose. Physicians or study coordinators at each study site will take a history from the patient prior to administration of the first dose of buprenorphine to document the time and date of last drug use and verify patient withdrawal status using the COWS and the ARSW. Moreover, a modified, three-day, rapid, buprenorphine induction procedure will be used with all patients in accordance with published guidelines ([name] *et al.*, 2000, in press 2000b). On day 1, patients will receive 2 sublingual tablets that each contains 2 mg of buprenorphine and 0.5 mg of naloxone, comprising a total dose of 4 mg of buprenorphine and 1.0 mg of naloxone. An additional 2 tablets (or 4 mg of buprenorphine and 1.0 mg of naloxone) may be provided if clinically warranted (i.e. if the patient presents with continued withdrawal signs and/or symptoms 1-2 hours following the initial 4 mg dose). Patients receiving BUP/NX will be instructed to hold the tablet(s) under their tongue until dissolved. The following shows the dose and schedule

for the first and remaining BUP/NX administrations over the course of the 13-day detoxification:

```
Day 1:
               4.0 mg buprenorphine – 1.0 mg of naloxone
               with an additional 4 mg/1 mg dose if needed
               8.0 \text{ mg buprenorphine} - 2.0 \text{ mg of naloxone}
Day 2:
Day 3:
               16.0 mg buprenorphine – 4.0 mg of naloxone
               14.0 mg buprenorphine – 3.5 mg of naloxone
Day 4:
               12.0 mg buprenorphine – 3.0 mg of naloxone
Day 5:
               10.0 mg buprenorphine – 2.5 mg of naloxone
Day 6:
               8.0 \text{ mg buprenorphine} - 2.0 \text{ mg of naloxone}
Day 7:
               6.0 mg buprenorphine – 1.5 mg of naloxone
Days 8-9:
Days 10 - 11: 4.0 mg buprenorphine – 1.0 mg of naloxone
Days 12 - 13: 2.0 \text{ mg buprenorphine} - 0.5 \text{ mg of naloxone}
```

11.5.2 Clonidine

Patients receiving oral clonidine will be instructed to swallow all pills and/or to leave their clonidine patch in place until replaced by medical personnel or until medical personnel directs the patient to change their dosage. The clonidine detoxification protocol was designed to reflect what is being used in clinical practice at a number of the participating CTP sites. Patients will be seen daily, on days of outpatient clinic operations.

In outpatient CTP sites, clonidine detoxification should be started early in the week (Tuesday or Wednesday [see section 11.4]) to insure a steady state level before the weekend with less medical staff. Medical personnel familiar with clonidine need to be available during clonidine treatment for daily patient monitoring, dose adjustment, and prescribing ancillary medication. Medical personnel should be familiar with monitoring vital signs for orthostatic changes and responding to any changes noted. Insure consistency in monitoring by using the same B.P. device at each visit.

Clonidine Dosing Procedure:

Day 1:

Encourage patients to drink lots of fluid. Dehydration exaggerates the hypotensive effects of clonidine. Before administering the test dose of clonidine, ask patients for any history of hypertension or hypotension, fainting or dizziness on rising. Take vital signs noting especially the systolic B.P. Check the EKG to insure the PR interval is not prolonged i.e. > .20 seconds. If the patient has systolic B.P. < 100 mm Hg or heart rate < 56 bpm, do not proceed with the clonidine test dose. Reassess patient if clinically warranted or discontinue the patient from the study.

Be cautious with patients with a history of hypertension or hypotension, fainting or dizziness on rising. Instruct all patients to get up slowly while taking clonidine (e.g. "sit up, swing your feet, and count to 10 before getting up").

If systolic B.P. is ≥ 100 mm Hg and pulse ≥ 56 bpm, give 0.1 mg oral clonidine test dose (0.05 mg for patients weighing less than 110 lbs,-0.2 mg for patients over 200 lbs). Check B.P. for orthostatic changes after 1 hour. The medical personnel should take B.P. after the patient is sitting for at least 3 minutes, and again after standing for 1 minute (note systolic B.P. and pulse). If systolic B.P. is ≥ 90 mm Hg and the pulse rate is ≥ 50 beats/min, put patient on a schedule of 0.1 mg clonidine q 4-6 hrs but do not exceed 0.6 mg for the first 24 hrs. If the systolic B.P. on recheck is < 90 mg Hg or the pulse rate is < 50 beats/min, instruct the patient to lie down and recheck the vital signs every hour until they return to normal (systolic B.P. ≥ 90 mm Hg and pulse rate is ≥ 50 beats/min). If the patient has symptomatic hypotension or bradycardia (i.e. syncope, dizziness, or chest pain) contact the physician and initiate the appropriate treatment. Treatment may include placing the patient in a recumbent position and beginning hydration with IV fluids.

Check the vital signs before each scheduled dose of clonidine. Skip the dose of clonidine if the systolic B.P. is < 90 mg Hg or the pulse rate is < 50 beats/min. Monitor for symptomatic hypotension, and adjust the dose if necessary. Drowsiness and orthostatic hypotension are common adverse effects of clonidine, requiring that the B.P. be monitored daily; however, these problems usually are not significant. Higher doses generally are needed for management of withdrawal than for treatment of hypertension.

Assuming that the patient tolerates clonidine well on the first day, apply clonidine patches in clinic according to the following weight schedule using TTS-1 patches:

| Weight | Clon | idine Patc |
|-------------|------|------------|
| < 110 lbs | 1-3 | TTS-1 |
| 110-200 lbs | 2-4 | TTS-1 |
| > 200 lbs | 2-6 | TTS-1 |

The clonidine patch is a 0.2 mm square that is applied in the same manner as a self-adhesive bandage. It is available in three sizes: 3.5, 7.0, and 10.5 cm². In a 24-hour period, these patches deliver an amount of clonidine equivalent to twice-daily dosing with 0.1, 0.2 or 0.3 mg of oral clonidine, respectively. Once the patch is placed on the epidermal surface, clonidine enters the circulatory system through the skin. A rate-limiting membrane within the patch governs the maximum amount absorbed. The patch supplies clonidine for up to 7 days. Only one strength will be used (0.1). Multiple patches can be placed on the patient's upper body, and removed if clinically indicated. (TIP series, number 19 reference).

Day 2:

It takes 2 days for the clonidine patches to achieve a maximum blood concentration; therefore, oral clonidine usually needs to be continued on Day 2. Therefore, oral clonidine may be administered on day 2 as clinically indicated, depending on vital signs and opiate withdrawal symptoms. The clonidine dose may be increased to either 0.2 mg q

6 hrs or 0.1 mg q 3 hrs (but not to exceed 0.8 mg qd) as long as the vital signs sitting and standing are normal. Apply caution, observation and same withholding rules as in Day 1.

Days 3-6

The patch(es) given on Day 1 will provide sustained blood levels of clonidine for up to 7 days. However, if the patient does not tolerate the patches (i.e., they have a rash or persistent hypotension), the patch(es) should be discontinued and oral clonidine administered in its place in doses similar to that given on Day 2, but with adjustments as clinically indicated, through Day 7. Vital signs (sitting and standing) will be checked on every scheduled clinic visit or as instructed by the treating physician.

Day 7

On Day 7, remove all clonidine patches. Evaluate the patient's tolerance of clonidine, vital signs sitting and standing, opiate use during the detoxification, and symptoms of opiate withdrawal to decide whether or not to replace the patches or continue with oral clonidine. A common course is to reduce the dose by one-half for the second week.

Days 8-13

Continue to monitor vital signs for any changes of B.P. and pulse. Discontinue clonidine administration and remove any remaining patches by Day 13.

Day 14

Monitor vital signs for any rebound elevation of B.P.

